## 8.4.2. Surveillance

### 8.4.2.1. Maternal participants

MA-RTI surveillance begins when a maternal participant enters the study and ends 6 months after delivery (Contact 1). It will be accomplished via contacts **initiated by maternal participants**.

*At study entry*, each **maternal participant** will be instructed to contact the site should she

- Visit (or plan to visit) a healthcare professional for any respiratory symptoms;
- Be hospitalized because of her respiratory symptoms.

If the study site is the primary treating facility for the maternal participant, a “contact” may also be made by going directly to the study site.

Site personnel will use a script to guide data collection once a contact has been made.

Due to the stop on study enrollment and vaccination, MA-RTI surveillance for the maternal participants will no longer be performed.

### 8.4.2.2. Infant participants

RTI surveillance in infant participants begins at birth (Visit 1-NB) and ends 12 months after birth (Visit 5-NB).

It will be accomplished via two types of contact and completion of diary cards

#### 8.4.2.2.1. RTI surveillance contacts

- In a **Passive** contact, the participant’s parent(s) / LAR(s) contact site personnel. Site personnel will use a script to guide data collection once a passive contact has been made.
- In an **Active** contact, site personnel contact the participant’s parent(s) / LAR(s). Active contacts will also be scripted.
  - *In regions where RSV transmission is seasonal, contacts should occur every week during the RSV season and every month outside the RSV season.*
  - *In regions with year-round RSV transmission, contacts will occur every 2 weeks.*
  - At least 3 attempts should be made within the week of a scheduled contact. If these attempts are unsuccessful, that active contact is considered a missed contact. The next active contact will be made according to schedule.

In special circumstances, such as for example, in the event of a pandemic, social distancing and confinement measures may considerably impact the region’s usual RSV

seasonality. Hence, frequency of active contacts may be temporarily adapted (in agreement with GSK and subject to IEC/IRB approval, as needed) to avoid unnecessary burden (Refer to Section 8).

Further details are provided in the SPM.

Site staff will use information gathered during each active or passive surveillance contact to determine whether a visit to assess a potential LRTI (Section 8.4.4) should be scheduled.

#### **8.4.2.2.2. RTI Diary cards**

Infant RTI diary cards will be provided to the infant participant's Parent(s)/LAR(s) as soon as possible after the infant's birth (ideally, at Visit 1 NB). Parents will use the diary card to document symptoms of the RTI.

Parent(s)/LAR(s) will be asked to bring any completed or partly completed diary cards with them to the infant participant's study visits (including any RTI assessment visits).

At each study visit/contact (including any assessment visits), RTI symptoms may have ended or may be ongoing. This will be evaluated in order to determine whether to retrieve the Diary Card and replenish the parent(s)/LAR(s)/designate(s) supply of blank cards as needed or, instruct them to continue collecting information until the corresponding symptom(s) have ended

- Completed RTI diary cards may be collected by study staff during a site visit, home visit, or via postal mail, whichever is most effective based on local practice.

Refer to the SPM for additional details.

#### **8.4.2.3. Maternal and infant participants**

If the maternal participant visited / the infant participant was taken to a healthcare provider not affiliated with the study, site personnel should (if permitted by local regulation) contact that healthcare provider to obtain the medical record(s) for the visit.

#### **8.4.3. When to conduct an assessment visit**

##### **8.4.3.1. For a maternal MA-RTI**

*Due to the stop on study enrollment and vaccination, MA-RTI surveillance for the maternal participants will no longer be performed.*

[figure not shown]
Conduct an assessment visit (Section 8.4.4), ideally within 3 calendar days after a medically attended visit due to RTI symptoms occurs during the surveillance period. However, a visit may be conducted *even beyond this window if symptoms are ongoing.*

If a maternal participant informs the site that she has RTI symptoms and (a) would seek / have sought medical advice for them and (b) is already scheduled for a study visit within the timeframes described above, then the site should perform the MA-RTI assessment visit procedures (including nasal swab) during the already scheduled study visit.

A decision tree is provided in [Figure 6](#).

Refer to the SPM for additional details regarding maternal MA-RTI surveillance.

**Figure 6 Decision Tree for site personnel – maternal surveillance and assessment**

**RR:** Respiratory rate; **SpO2:** Blood oxygen saturation by pulse oximetry.

Includes cases where symptoms would have resulted in a medically attended visit if participant were not already scheduled for a study visit

Details regarding the RTI assessment visit are provided in [Section 8.4.4](#) and the SPM.

#### 8.4.3.2. For an infant RTI

Conduct an assessment visit, as described in Section 8.4.4, as soon as possible after at least one of the following has been reported during the surveillance period:

- Difficulty in breathing,
- Wheezing
- The maternal participant/LAR intends to seek medical care because of concern about the infant's respiratory tract illness, or general health in the context of the infant's respiratory tract illness.

[figure not shown]
The visit should take place as soon as possible; ideally within 3 calendar days. However, a visit may be conducted *even beyond the specified ideal window* if symptoms are ongoing.

- After the first assessment visit, site personnel should use results of additional contacts to assess the development of new and worsening of previously reported symptoms.
- Site personnel should conduct a **follow-up** assessment **visit** as soon as possible after learning:
  - that any symptom present at the first assessment visit has worsened, OR
  - that there are new symptoms of difficulty in breathing or wheezing, OR
  - that there is new or increased parental concern in the context of the respiratory tract illness.

The timing of the follow-up visit should be consistent with the guidance given above.

A decision tree is provided in [Figure 7](#). Refer to the SPM for additional details regarding infant RTI surveillance.

**Figure 7 Decision Tree for site personnel - infant surveillance and assessment**

**RR:** Respiratory rate; **SpO2:** Blood oxygen saturation by pulse oximetry.

Details regarding Surveillance are provided in Section 8.4.2.2 and the SPM.

Cough, runny nose, blocked nose, difficulty in breathing, wheezing are described in Section 8.4.1.2

Details regarding the RTI assessment visit are provided in Section 8.4.4 and the SPM.

Post-visit follow up is described in Sections 8.4.6 and in the SPM.

If a follow-up assessment visit is conducted, collection of additional nasal swabs is as described in Table 14.

Parental concern *in the context of an RTI*

#### 8.4.4. Assessment visit procedures

The purpose of each assessment visit is to objectively document signs and symptoms of a respiratory tract illness by an appropriately qualified person (i.e. medical or nursing), provide medical advice or referral as appropriate, and collect specimens for detection of RSV infection.

An assessment visit may take place at the investigator's clinical facility or another medical facility, or via a home visit by qualified site staff (or a designated third party), as appropriate per the judgment of the investigator (and as allowed by local law).

**Note that if the reported symptoms are severe enough to warrant urgent care, the participant / parent(s)/LAR(s) should be advised to seek such care (e.g. Emergency Room).**

##### 8.4.4.1. Clinical evaluation

At every assessment visit, the investigator/study staff/designated third party will evaluate the clinical signs and symptoms of the RTI. Data to be collected and recorded include (but are not limited to):

**For maternal participants:** Due to the stop on MA-RTI surveillance for maternal participants, these checks will no longer be performed.

- Temperature
- Respiratory rate
- Blood oxygen saturation measured by pulse oximetry (in room air, if feasible), see further details in Section [8.2.1.2.1](#)
- Results of chest auscultation
- Signs of difficulty in breathing (wheezing and tachypnoea in maternal participants)

**For infant participants:**

- Temperature
- Respiratory rate
- Blood oxygen saturation measured by pulse oximetry (in room air, if feasible), see further details in Section [8.2.1.2.1](#)
- Results of chest auscultation
- Presence of cough, runny nose or blocked nose
- Signs of difficulty in breathing (wheezing, tachypnoea, nasal flaring, chest in-drawing and apnea)
- Irritability/agitation
- Lethargy/excessive sleepiness
- Cyanosis
- Feeding poorly

**8.4.4.2. Nasal swab collection**

Refer to [Table 12](#) (maternal participants) and [Table 14](#) (infant participants). Additional details are provided in the SPM.

**8.4.4.3. Missed assessment visit**

If the criteria for an assessment visit have been met but the visit cannot take place while symptoms are ongoing, it is a missed assessment visit.

If it is truly not possible to perform an assessment visit (for example, if the participant develops a MA-RTI\* or potential RTI/LRTI while the family is travelling, and all symptoms have resolved by the time the family returns), then the corresponding assessment visit page of the eCRF should be filled in as completely as possible using available medical history and medical records.

*\* Due to the stop on study enrollment and vaccination, MA-RTI surveillance for the maternal participants will no longer be performed.*

**8.4.5. RTI hospitalization during the surveillance interval**

Whenever a participant is admitted to hospital for observation or treatment of an acute respiratory illness during the surveillance interval for that participant, a nasal swab should be collected using GSK-provided supplies and sent to GSK for analysis, as described in [Table 12](#) and [Table 14](#).

**8.4.6. Follow-up of infant respiratory tract illnesses**

Any infant RTI documented as ongoing at a previous visit/contact will be reviewed at subsequent visits/contacts during the surveillance interval until (a) all symptoms have resolved (except runny nose, often chronic in infants), or (b) the participant completes Visit 5-NB or (c) the participant is lost to follow up.

**8.4.7. Covid-19 Infection**

Maternal and infant COVID-19 cases identified during the study (as per standard of care) will be captured and reported using standard AE, medically-attended AE or SAE criteria, as outlined in [Section 10.3](#).

COVID-19 cases should be reported in the eCRF according to the WHO Case Definition [[WHO, 2020](#)] using one of the following terms:

- Suspected COVID-19 infection
- Probable COVID-19 infection
- Confirmed COVID-19 infection

**8.5. Treatment of overdose**

Not applicable.

**8.6. Pharmacokinetics**

Not applicable.

**8.7. Pharmacodynamics**

Not applicable.

**8.8. Genetics**

Not applicable.

**8.9. Biomarkers**

Not applicable.

**8.10. Health outcomes**

Not applicable.

**9. STATISTICAL CONSIDERATIONS****9.1. Statistical hypotheses**

There are no hypotheses test for vaccine efficacy endpoints.

**9.2. Sample size determination**

Note: A total of 5328 participants have been enrolled and vaccinated in the study so far, and there will be no new maternal participants vaccinated. Please refer to Section 2.3 for details. However, monitoring will continue for rest of the study period. All planned objectives will be assessed for the participants enrolled so far.

**9.3. Populations for analyses (Amended 23 February 2023)****Table 22 Maternal participants**

	Description
Analysis Set	Maternal participants
Enrolled	All maternal participants who completed the informed consent process and signed the informed consent form.
Exposed	All maternal participants who received the study intervention. The allocation in a group is done in function of the administered intervention.
Per Protocol – Immunogenicity	All maternal participants who received the study intervention to which they were randomised and have post-vaccination data minus participants with protocol deviations that lead to exclusion.
Solicited Safety – Stage A only	All maternal participants in the Exposed Set who have solicited safety data

**Table 23 Infant participants**

Analysis Set	Description
Exposed	Infants live-born to exposed maternal participants, whose parents/LARs completed the informed consent process and signed the informed consent form
Per Protocol – Immunogenicity	All infant participants in the Exposed set minus those who (a) were born less than 4 weeks post- maternal participant vaccination and/ or (b) have protocol deviations that lead to exclusion.
Full Analysis – Efficacy	All infant participants in the Exposed set.
Modified Full Analysis – Efficacy	All infant participants in the Exposed set who were born after at least 4 weeks of vaccination.
Per Protocol – Efficacy	All infant participants in the Modified Full Analysis – Efficacy set minus those who have protocol deviations that lead to exclusion.

**9.3.1. Criteria for elimination from analysis**

The Statistical Analysis Plan (SAP) will provide a complete list of criteria for elimination from the analysis sets. Criteria may include, but are not limited to, those in Sections [9.3.1.1](#) and [9.3.1.2](#).

**9.3.1.1. Intercurrent medical conditions and concomitant medications / products / vaccines that may lead to elimination of a participant (maternal/infant) from per-protocol analyses (efficacy/immunogenicity)****9.3.1.1.1. Maternal participants**

- Any of the medications listed in Section [5.2.1.2](#) if administered up to Delivery (Visit 3), except corticosteroids for fetal lung maturation administered after study vaccination.

**9.3.1.1.2. Infant participants**

- **For the efficacy analyses:**
  - Systemic immunosuppressants or other immune-modifying drugs administered chronically (i.e. for more than 14 consecutive days).
    - For corticosteroids, this will mean prednisone or equivalent,  $\geq 0.5$  mg/kg/day.
    - Topical steroids are allowed.
    - Inhaled steroids are allowed if used in accordance with local labelling information (e.g. for budesonide).
  - RSV-specific immunoglobulins at any time during the study
- **For the immunogenicity analyses:** Immunoglobulins and/or any blood or plasma derivatives administered up to Day 43 post birth (Visit 2-NB), or Day 121 post birth (Visit 3-NB), or Day 181 post-birth (Visit 4-NB), depending on the infant's assigned sub-cohort for blood sampling.

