Infant	2010	Protocol violation (inclusion/exclusion criteria)						Y			Y
Infant	2050.Vx	Intercurrent medical conditions which are exclusionary as per protocol						Y			Y
Infant	2090.Vx	Participant did not comply with blood sample schedule						Y			

CONFIDENTIAL

212171 (RSV MAT-009)
Statistical Analysis Plan Amendment 5

	Code	Description	Maternal analysis set				Infant analysis set				
			Enrolled	Exposed	Per Protocol - Immunogenicity	Solicited Safety	Exposed	Per Protocol - Immunogenicity	Modified Full Analysis - Efficacy	Full Analysis - Efficacy	Per Protocol - Efficacy
Determined in mother or infant											
Infant	2100.Vx	Serology result not available (immunogenicity sample collected but invalid/no result)						Y			
Infant	2120.Vx	Obvious incoherence or abnormality or error in the data						Y			
Infant	2130.Vx	Testing performed on serology samples not aligned with ICF						Y			
Infant	2131.Vx	Testing performed on nasal samples not aligned with ICF									Y
Infant	2110.Vx	Immunogenicity sample collected but GSK decided not to test						Y			
Infant	2040.Vx+, 2040#	Administration of any medication/product forbidden by the protocol (leading to elimination from PPS-E and PPS-I)						Y			Y
Infant	2140Vx+	Administration of any medication/product forbidden by the protocol (leading to elimination from PPS-I)						Y			
Infant	2240	Administration of any medication/product forbidden by the protocol (leading to elimination from PPS-E)									Y

CONFIDENTIAL

212171 (RSV MAT-009)
Statistical Analysis Plan Amendment 5

Determined in mother or infant	Code	Description	Maternal analysis set				Infant analysis set				
			Enrolled	Exposed	Per Protocol - Immunogenicity	Solicited Safety	Exposed	Per Protocol - Immunogenicity	Modified Full Analysis - Efficacy	Full Analysis - Efficacy	Per Protocol - Efficacy
Infant	2060.Vx, 2060#	Concomitant infection related to the vaccine which may influence immune response						Y			Y
Infant	2070.Vx, 2070#	Concomitant infection not related to the vaccine but may influence immune response						Y			Y
Infant	3100	Birth is less than 4 weeks post-vaccination						Y	Y		Y

* in case a mother withdraws consent or does not consent for the baby, we still report SAEs/AESIs for the infants if collected

.Vx indicates participants whose data will be eliminated from a specific endpoint/visit

[figure not shown]
.Vx+ indicates participants whose data will be eliminated from a specific endpoint/visit onwards

Y indicates exclusion

[figure not shown]

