4.2.3. Elimination from Full Analysis Set for Efficacy (FAS-E)

4.2.3.1. Excluded Infants from Full Analysis Set for Efficacy

An infant will be excluded from the FAS efficacy analysis under the following conditions:

Code	Condition under which the code is used	Visit (timepoints) where the code is applicable
800, 800#	Fraudulent data	All
900, 900#	Invalid informed consent	All
1030#	Study vaccine not administered	All

Carry forward elimination from mother to infant

4.2.4. Elimination from Per protocol analysis set for Efficacy (PPS-E)**4.2.4.1. Excluded Infants from Per protocol analysis set for Efficacy (PPS-E)**

A participant will be excluded from the PPS efficacy analysis under following conditions:

Code	Condition under which the code is used	Visit (timepoints) where the code is applicable
800, 800#	Fraudulent data	All
900, 900#	Invalid informed consent	All
1030#	Study vaccine not administered	All
3100	Birth/Delivery is less than 4 weeks post-vaccination	All
1040#	Administration of concomitant vaccine(s) forbidden in the protocol	All
1050#	Randomisation failure	All
1060#	Randomisation code was broken	All
1070#	Mother got vaccinated with the correct vaccine but containing an incorrect volume	All
1070#	Vaccination not according to protocol (site of injection, route of administration, wrong replacement of study treatment administered)	All
1070#	Study treatment not prepared as per protocol (e.g. reconstitution)	All
1070#	Other deviations related to wrong study treatment/administration/dose	All
1070#	Study treatment administered while contraindicated	All
1080#	Vaccine temperature deviation	All
1090#	Expired vaccine administered	All
2010, 2010#	Protocol violation (inclusion/exclusion criteria)	All
2040*	Administration of any medication/product forbidden by the protocol (leading to elimination from PPS-E and PPS-I)	All
2240*	Administration of any medication/product forbidden by the protocol (leading to elimination from PPS-E)	All
2040*	Administration of any medication/product forbidden by the protocol (leading to elimination from PPS-E and PPS-I)	All
2050.Vx*	Intercurrent medical conditions/concomitant medications which are exclusionary as per protocol	All

Code	Condition under which the code is used	Visit (timepoints) where the code is applicable
2050#*	Maternal intercurrent medical conditions which are exclusionary as per protocol	All
2060#* 2060*	Concomitant infection related to the vaccine which may influence immune response	All

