2070#* 2070*	Concomitant infection not related to the vaccine but may influence immune response	All
2120.Vx	Obvious incoherence or abnormality or error in data	All
2131.Vx	Testing performed on nasal samples not aligned with ICF	All

.Vx indicates participants whose efficacy data will be eliminated from a specific endpoint

Carry forward elimination from mother to infant

* Attribution of these elimination codes to participant need CRDL review of individual listing

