2110.Vx	Immunogenicity sample collected but GSK decided not to test	Visit 1/Day 1 Visit 2/Day 31, Visit 3/Delivery

* Attribution of these elimination codes to participant need CRDL review of individual listing
.Vx+ indicates participants whose immunogenicity data will be eliminated from a specific visit onwards;
.Vx indicates participants whose immunogenicity data will be eliminated from a specific visit.

4.2.5.2. Excluded participants from Per-protocol immunogenicity (PPS-I) analysis set of infant participants

An infant participant will be excluded from the PPS immunogenicity analysis under following conditions:

Table 8 Elimination code and condition for infant participants

Code	Condition under which the code is used	Visit (timepoints) where the code is applicable
800, 800#	Fraudulent data	All
900, 900#	Invalid informed consent	All
1030#	Study vaccine not administered	All
1040.Vx##+*	Administration of concomitant vaccine(s) forbidden in the protocol	All
1050#	Randomisation failure	All
1060#	Randomisation code was broken	All
1070#*	Mother got vaccinated with the correct vaccine but incorrect volume	All
1070#*	Vaccination not according to protocol (site of injection, route of administration, wrong replacement of study treatment administered)	All
1070#*	Study treatment not prepared as per protocol (e.g. reconstitution)	All
1070#*	Other deviations related to wrong study treatment/administration/dose	All
1070#*	Study treatment administered while contraindicated	All
1080#	Vaccine temperature deviation	All
1090#	Expired vaccine administered	All
2010, 2010#	Protocol violation (inclusion/exclusion criteria)	All
2040#*	Administration of any medication/product forbidden by the protocol	All
2140.#*	Administration of any medication/product forbidden by the protocol	All
2040Vx*	Administration of any medication/product forbidden by the protocol	Visit 1-NB/Birth Visit 2-NB/Day 43 post-birth ^a Visit 3-NB/Day 121 post-birth ^a Visit 4-NB/Day 181 post-birth ^a
2140Vx*	Administration of any medication/product forbidden by the protocol (leading to elimination from PPS-I)	Visit 1-NB/Birth Visit 2-NB/Day 43 post-birth ^a Visit 3-NB/Day 121 post-birth ^a Visit 4-NB/Day 181 post-birth ^a

CONFIDENTIAL

212171 (RSV MAT-009)
Statistical Analysis Plan Amendment 5

Code	Condition under which the code is used	Visit (timepoints) where the code is applicable
2050.Vx#*	Intercurrent medical conditions which are exclusionary as per protocol	All

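### An infant can be dropped from the whole per-protocol efficacy set because of RSV immunoglobulin or prolonged immunosuppressants started after the RSV LRTI or after month 6

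*Protocol*

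**What the plan says.** Protocol 9.3.1.1 has a permissive heading. It covers "concomitant medications / products / vaccines that may lead to elimination of a participant (maternal/infant) from per-protocol analyses (efficacy/immunogenicity". Within it, 9.3.1.1.2 names two product classes for the infant efficacy analyses: "Systemic immunosuppressants or other immune-modifying drugs administered chronically (i.e. for more than 14 consecutive days", and "RSV-specific immunoglobulins at any time during the study". Neither entry refers to the date of an RSV LRTI, the reason for treatment, or the 6-month limit of the primary endpoints.

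Protocol 9.3.1 leaves the complete list of criteria to the SAP. SAP 4.2.4.1 is firmer: "A participant will be excluded from the PPS efficacy analysis under following conditions". Its list includes code 2240, "Administration of any medication/product forbidden by the protocol (leading to elimination from PPS-E" only, and code 2040, which covers both per-protocol sets. Both are shown without a .Vx suffix and at all timepoints. Both are starred, and the star means "Attribution of these elimination codes to participant need CRDL review of individual listing". No criteria for that review are given.

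SAP Table 6 lists 2240 without a suffix as well, but lists infant code 2040 with .Vx+. The table footnote explains that suffix: "Vx+ indicates participants whose data will be eliminated from a specific endpoint/visit onwards".

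PPS-E and FAS-E complement the primary analysis, which uses modified FAS-E (SAP 5.2.1). Infant secondary efficacy uses modified FAS-E (SAP 5.2.2).

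**The concern.** A per-protocol exclusion is meant to remove infants whose exposure was altered before the outcome could be observed. A product given after the RSV LRTI, possibly because of it, cannot have altered that outcome. Eliminating on it means that set membership depends partly on the outcome.

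Two situations are open under the wording. An infant with an RSV LRTI at month 2 and a qualifying product at month 3 can lose the case and all follow-up. An infant treated only in months 7 to 12 can be removed from a birth-to-6-month analysis.

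At stake is whether PPS-E can do its job of supporting or challenging the primary VE estimate. With few severe cases expected, a single removal can visibly move the PPS-E figure.

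**Working it through.** **1. Text check.** The rules compare as follows.

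| Rule | Place | Time limit |
|---|---|---|
| RSV immunoglobulin, efficacy | Protocol 9.3.1.1.2 | None; the whole study |
| Immunosuppressants over 14 days, efficacy | Protocol 9.3.1.1.2 | None stated |
| Immunoglobulins and blood products, immunogenicity | Protocol 9.3.1.1.2 | Up to the infant's assigned sampling visit |
| Other investigational products | Protocol 9.3.1.1.3 | Within the analysis interval |
| Codes 2040 and 2140, PPS-I | SAP Table 8 | Visit-specific entries (Vx) |
| Code 2240, PPS-E | SAP Table 6 and 4.2.4.1 | None; no suffix, all timepoints |
| Infant code 2040, PPS-E | SAP Table 6 against 4.2.4.1 | .Vx+ in one, no suffix in the other |

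The mechanism for a time limit exists, and other codes in the PPS-E list use it: 2050, 2120 and 2131 carry .Vx, which the footnote to 4.2.4.1 ties to a specific endpoint. Code 2240 does not. For 2040 the two places contradict each other. Nothing says whether RSV immunoglobulin receives 2040 or 2240. Nothing keeps a case that came before treatment, or ends an infant's PPS-E follow-up at treatment.

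**2. Figures in the plan.** The documents give no number of infants expected to receive these products and no PPS-E size or power, so there is nothing to reproduce. The rest is illustration.

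**3. Inputs.**
- Infants: 3496 active; 5235 − 3496 = 1739 control (Protocol 2.3).
- Attack rates: 1% severe and 3% any severity (titles of the operating-characteristics tables in the protocol's list of tables), taken as control rates by assumption.
- VE: 70% severe and 50% any severity (Protocol 4.2.5).
- Share of cases removed: not in the documents; 5 to 20% tried.

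**4. Expected cases.**
- Severe: control 1739 × 0.01 = 17.39; vaccine 3496 × 0.01 × 0.30 = 10.49.
- Any severity: control 1739 × 0.03 = 52.17; vaccine 3496 × 0.03 × 0.50 = 52.44.

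**5. Effect of removal.** VE = 1 − (vaccine cases / vaccine infants) / (control cases / control infants), with removed infants taken from both cases and denominators.

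| Cases removed | Severe VE at 5, 10, 20% | Any-severity VE at 5, 10, 20% |
|---|---|---|
| Equal share, both arms | 70.0, 70.0, 70.0% | 50.0, 50.1, 50.2% |
| Control only | 68.4, 66.7, 62.6% | 47.4, 44.6, 37.9% |
| Vaccine only | 71.5, 73.0, 76.0% | 52.5, 54.9, 59.9% |

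One severe case removed:
- from control: 1 − (10.488/3496) / (16.39/1738) = 68.2%;
- from vaccine: 1 − (9.488/3495) / (17.39/1739) = 72.9%.

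Bias needs differential removal and can go either way.

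**The case against.** The strongest case against acting has four parts.

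*Elimination is discretionary.* A reader might infer that every treated infant is deleted. The documents do not support that: the protocol heading is permissive, the starred codes need CRDL review, and Table 6 gives 2040 a from-a-visit-onwards form. This stands, and the point is therefore that an infant can be removed. It does not dispose of the matter, because the review has no written timing criterion and the study is unblinded (Protocol 6.3.6 and 8.2.3; SAP 8).

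*The reach is small.* Modified FAS-E and FAS-E carry no such exclusion, there are no efficacy hypothesis tests (Protocol 9.1), VE is descriptive (SAP 8), and development has been discontinued (Protocol 2.3). All of this stands.

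*Any imbalance is speculative.* A reader might infer that the deletions favour one arm, because preterm birth was commoner in the vaccine arm and preterm infants may receive these products more often. The documents say nothing about use of the products. Even a generous version moves little. The reported RR of 1.38 (1.08 to 1.75) gives SE(log RR) = ln(1.75/1.08)/3.92 = 0.123, which implies about 236 and 85 preterm births. If 20% were treated (an assumption), about 47 and 17 infants would go. Removed as non-cases, with 10 and 17 severe cases, VE changes from 1 − (10/3496)/(17/1739) = 70.7% to 1 − (10/3449)/(17/1722) = 70.6%. The base is also too large, since births under 4 weeks after vaccination are already outside PPS-E (code 3100). Eliminating infants for prophylaxis given before any case is an ordinary per-protocol choice. Only treatment after the case selects on outcome.

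*It is late.* SAP 7.1 reports that the 6-month analysis, covering the primary efficacy endpoints, has taken place, and its description of the final analysis names secondary but not primary efficacy. Treatment in months 7 to 12 matters only where it was already recorded at that cut, or if PPS-E is derived again. This stands and shapes the fix.

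**Conclusion.** The concern holds in a limited form. The written criteria allow removal from the whole of PPS-E for treatment that began after the endpoint or outside its window. For code 2240 this follows directly from the text. For code 2040 the SAP contradicts itself, and the code for RSV immunoglobulin is unspecified. For immunosuppressants the lack of a window is read from silence, whereas for RSV immunoglobulin it is explicit.

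The consequence is confined to the complementary PPS-E analysis of the two primary endpoints. How many infants were affected, in which arm, and in which direction VE would move cannot be known from the documents. The illustrative shifts rest on planning attack rates, target VE and assumed one-sided removal; they show sensitivity, not expected bias. The primary VE method and the missing-data rules are redacted, so whether they already deal with this cannot be checked.

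**What to change.** In SAP Table 6 and 4.2.4.1:

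- Reconcile the two entries for infant code 2040, and state which code RSV immunoglobulin and prolonged immunosuppressants each receive.
- Make 2040 and 2240 endpoint-specific for PPS-E. Only products started before the infant's first case of the endpoint, and inside that endpoint's window (birth to 6 months), should lead to elimination.
- Record this as the criterion for the CRDL review.
- Report by arm the number of infants affected, split by whether treatment began before or after a case.

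Because the 6-month analysis has been run, show the re-derived PPS-E result beside the one already produced and label it post hoc.

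Censoring at the first dose, instead of deleting infants treated before a case, is optional. It would treat eventual cases and non-cases alike, but whether it fits depends on the redacted VE method.

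The cost is SAP wording, one derivation from medication records already required by Protocol 6.5.2 and 6.5.3, and one supplementary table. No new data are needed. If no infant was removed for treatment after a case or after month 6, a sentence saying so is enough.
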